16.0 Potential Benefits to Subjects*

- *Describe the potential benefits that individual subjects may experience from taking part in the research. Include as may be useful for the IRB's consideration, the probability, magnitude, and duration of the potential benefits.*
 - The current method of creating and maintaining a circulating warm water bath is arduous, time consuming, and not controlled. It is highly suspected that the research method of water bath management will be quicker to achieve target water temperatures, safer in that the water temperature will be electronically monitored and maintained, and will benefit the patient in the expedited thawing of the frozen tissue.

17.0 Data Management* and Confidentiality

- *Describe the data analysis plan, including any statistical procedures or power analysis.*
 - The primary outcomes are whether or not the tissue rewarmed and the ability of the SVD to maintain accurate target water temperature. Descriptive statistics will be performed to describe the patient population, time to rewarm, and the provider assessment of ease of use.
- *Describe the steps that will be taken to secure the data (e.g., training, authorization of access, password protection, encryption, physical controls, certificates of confidentiality, and separation of identifiers and data) during storage, use, and transmission.*
 - Paper data collection forms will be kept in a locked office until transferred by the PI to a Microsoft excel file on a password-protected computer. The identifiers and data will be contained in two separate files. Only the PI and sub-investigators will have access to the de-identified data and the PI will retain sole access to the identification key.
 - Data from other sites will be uploaded directly into REDCap database hosted by DHMC to ensure secure data transfer for multicenter analysis. Access to the data on the

PROTOCOL TITLE: Assessment of Sous Vide Water Baths for Acute Rewarming of Frostbitten Extremities.

REDCap database will be restricted to the PI and DHMC study staff.

- *Summarize the record retention plan applicable to the study (taking into account any applicable Dartmouth Department, Division or Research Center requirements, or applicable funding sponsor requirements.)*
 - Records will be stored on-site on the PI's password protected computer for 3 years after publication.
 - *Describe any procedures that will be used for quality control of collected data.*
 - Dual thermometers will act as redundant sampling of water bath temperatures
 - *Describe how data or specimens will be handled study-wide:*
 - *What information will be included in that data or associated with the specimens?*
 - The data collection form will include the MRN of the patient and a numeral used to de-identify the data in the excel file. The collection form will contain a table of recorded water temperatures, including a temperature from each of the two thermometers as well as the SVD every 2 minutes during the rewarming period. Any adverse events will also be recorded.
 - *Where and how data or specimens will be stored?*
 - Data collection forms filled out by clinicians or investigators will be stored in a locked office until the data is transferred to a Microsoft excel file. The data file will be stored on the password-protected computer of the PI.
 - *How long the data or specimens will be stored?*
 - Data will be stored throughout the duration of the study and manuscript preparation.
 - *Who will have access to the data or specimens?*
 - The data collection forms will be accessible to the clinician filling it out. Once transferred to excel format, only the PI and sub-investigators will have access to the de-identified data. Only the PI and key study personnel will have access to the de-identification number key.

PROTOCOL TITLE: Assessment of Sous Vide Water Baths for Acute Rewarming of Frostbitten Extremities.

- *Who is responsible for receipt or transmission of the data or specimens?*
 - Data collection forms will be deposited in the locked office by the clinician or investigator filling out the form during active rewarming of a subject.
 - Data will be entered into REDCap for further analysis.
 - External sites will enter their data directly into the DH REDCap Database
- *How data or specimens will be transported?*
 - Data will remain on the password protected hard drive of the PI.
 - Deidentified data may be analyzed by additional research team members.

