6.0 Procedures Involved*

- Patients presenting to the ED at Dartmouth-Hitchcock and external study sites with acute frostbite (tissue still frozen) of the hands and/or feet will be identified and approached for recruitment. Patients not entering the study will continue to be treated by ED providers in the traditional fashion.
- Patients recruited for the SVR study will be consented to have their circulating warm water bath(s) heated by the novel SVR method. Providers or nurses caring for the study subjects will be consented to participate and will 1) conduct the SVR procedure, and 2) complete a questionnaire. A researcher will gather SVR equipment and attach two thermometers on the basin: one on the side nearest the SVD, the other on the opposite side. The researcher will verbally walk the provider or nurse carrying out the SVR through the following steps. A 15 L Sterilite® basin will be filled to the marked line (12cm) with water from jugs at room temperature, for each frozen extremity. One extremity can be rewarmed in a single basin, with the possibility for up to four simultaneous SVR basins for a patient with frostbite of all hands and feet. The SVD will be attached to the distal edge of the basin, with one SVD per rewarming basin. The SVD will be turned on and set to maintain the bath at a constant 38°C for 30 minutes duration. The thermometers will be powered on continuously and the researcher will record temperatures simultaneously from each thermometer and the SVD every 2 minutes. At the end of the 30 minute treatment, the extremity will be assessed by the researcher for warmth and pliability. If the extremity still feels cold or frozen, an additional 30 minutes in the water bath will commence, with

PROTOCOL TITLE: Assessment of Sous Vide Water Baths for Acute Rewarming of Frostbitten Extremities.

subsequent reassessment. Rewarming will be considered complete when the affected tissue becomes red or purple, soft, and pliable.

- Patients who do not consent to SVR and elect for traditional water bath management will be asked for their consent to record the similar demographic, water temperature, and time-to rewarm data as in the SVR treatment arm. After re-warming is complete, the provider will be asked to fill out a survey regarding the ease of use and efficacy of the SVR.
- *Describe:*
 - *Procedures performed to lessen the probability or magnitude of risks.*

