 - Dual thermometers will record water bath temperature to assess for the possibility of disequilibrium in water temperature and to detect possible hot spots.
 - The treatment will be terminated if two consecutive thermometer recordings detect water temperatures of 42°C or above.
 - The rewarming process in acute frostbite is inherently painful. Pain increases when water bath temps are above 40°C. No additional discomfort is expected beyond that for frostbite rewarming, at the target temperature of 38°C. The provider can provide analgesia as indicated. The treatment will be terminated if the patient has discomfort that is deemed by the treating provider to be above that expected from rewarming frozen tissue.
 - If treatment is discontinued prior to successful rewarming, standard rewarming will occur.
 - *Explain if any part of this study involves the use of procedures that are inconsistent with the standard of care at Dartmouth-Hitchcock Medical Center.*
 - There are no parts of the study that are inconsistent with the standard of care at DHMC. The novel treatment is to assess a treatment modality that may elevate the standard of care.
 - *All drugs and devices used in the research and the purpose of their use, and their regulatory approval status.*

PROTOCOL TITLE: Assessment of Sous Vide Water Baths for Acute Rewarming of Frostbitten Extremities.

- The ANOVA Precision® Cooker is a purpose-built device to maintain a set temperature circulating water bath. The device is not FDA approved for medical use. There will be no use of a placebo.
- The study treatment takes place entirely in the ED, which allows for comprehensive assessment of protocol compliance. If a subjects opts to discontinue participation at any time during the rewarming, standard techniques for maintaining the water bath will replace the SVD.
- *Describe randomization:*
 - All patients presenting with acutely frostbitten hands or feet will be approached for inclusion in the study. There is no randomization. Any patient not consenting to the use of the SVD but willing to allow data collection will act as a control group.
- *Prior and Concomitant Therapy:*
 - Concomitant therapies, such as intravenous fluids, anti-emetics, forced air warming blanket, and analgesia, as well as other medications deemed necessary by the provider, may be given concomitantly during the treatment period.

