 - The blood pressure cuff used in the standard emergency department assessment of vital signs will be placed on an extremity that is not currently being rewarmed, whenever possible, to avoid constricting blood flow to the affected tissue.
- *Data Collection:*
 - Prior to rewarming, physical examination of the patient, including the frozen extremity, will be completed and documented in the EPIC/EMR chart by the provider.
 - Two thermometers, placed in the rewarming basin, will continuously monitor the water temperature. The temperature reading on both thermometers as well as the SVD will be recorded on a paper data sheet by a trained provider at 2-minute intervals until the 30 minutes of treatment are complete.

PROTOCOL TITLE: Assessment of Sous Vide Water Baths for Acute Rewarming of Frostbitten Extremities.

- The researcher will repeat an exam, assessing all extremities being treated by SVR, at 30 minutes to determine warmth and pliability of the tissue, confirming thaw. Rewarming will be considered complete if the affected tissue becomes red or purple, soft, and pliable. The same rewarming criteria applies for all extremities.
 - The provider will be asked to fill out a survey on all acute frostbite patients whom consent to the study protocol, as well as those that do not.
 - *The source records that will be used to collect data about subjects. (Attach all surveys, scripts, and data collection forms.) If there are plans for long-term follow-up (once all research related procedures are complete), what data will be collected during this period.*
 - The patient's age and sex will be recorded. The physical examination and pertinent medical information will be reviewed to confirm the location and extent of the frostbite and for contributing conditions.
 - Demographics and relevant medical history will be accessed.
 - Please see attached surveys and data collection forms.
 - Enrolled subjects may be contacted via phone and myDH or local electronic medical record communication at 6 months post-enrollment to assess long term outcomes of their frostbite. Chart review to assess related complications will also occur at this time.
 - *Explain if any part of this study involves genetic analysis of biological specimens. If yes, explain whether the study is based on one the following:*
 - This study does not involve genetic analysis of biological specimens.

Provider Participation:

- *Role/Activities:*

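### The two thermometers are called redundant but sit on opposite sides of the basin, so a steady near-far difference mixes true gradient with sensor offset

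*Combined protocol and SAP*

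**What the plan says.** Section 17.0 (Data Management and Confidentiality) answers its prompt on quality control of collected data with one line: "Dual thermometers will act as redundant sampling of water bath temperatures".

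Section 6.0 (Procedures Involved) has the researcher "attach two thermometers on the basin: one on the side nearest the SVD, the other on the opposite side". Its list of risk-reducing procedures gives the reason: the thermometers are there to "assess for the possibility of disequilibrium in water temperature and to detect possible hot spots".

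The data form holds a table of readings, "including a temperature from each of the two thermometers as well as the SVD every 2 minutes during the rewarming period". Section 6.0 has these recorded "at 2-minute intervals until the 30 minutes of treatment are complete". Each basin starts "filled to the marked line (12cm) with water from jugs at room temperature".

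Section 17.0 names two primary outcomes: whether the tissue rewarmed, and whether the device holds the bath accurately at its target. The set point is 38°C. The documents state no thermometer accuracy, no pre-use or calibration check, no agreement tolerance, no rule for discordant readings, and no statement of which of the three readings defines the bath temperature.

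**The concern.** The same two sensors are given two jobs that need different arrangements. To act as replicates they must read the same water, so that any disagreement is sensor error. To detect a hot spot they must read different water, so that disagreement is the finding. The plan adopts the second arrangement and claims the benefit of the first.

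At stake is how the temperature data can be interpreted. A fixed offset in one thermometer could be reported as an uneven bath, or could cancel a real unevenness and hide it. Section 2.0 expects 5-20 cases in all and section 12.0 expects 1-5 per site. If a site reuses one pair of thermometers (the documents do not say), the same offset recurs in every patient there and does not average out. Readings also feed the 42°C termination rule (sections 4.0, 6.0 and 14.0) and the below-37°C rule (section 15.0), although the effect on those rules has not been quantified.

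**Working it through.** The plan has no figure to reproduce. The check has two parts: what the recorded readings can identify, and how large the ambiguity could be.

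**1. What can be identified**

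Let μ be the mid-bath temperature, g the true near-minus-far gradient, and b a constant bias for each sensor. Assume that the sous vide device (SVD) senses the water at its own end.

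- near = μ + g/2 + b_near
- far = μ − g/2 + b_far
- SVD = μ + g/2 + b_svd

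Differences:

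- near − far = g + (b_near − b_far). Only this sum can be estimated, and neither part separately.
- near − SVD = b_near − b_svd. This compares the near thermometer with the display. It says nothing about b_far, so g remains confounded.

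More readings do not help. Every 2 minutes over 30 minutes gives 15 time points (16 with time zero), hence 3 × 15 = 45 or 3 × 16 = 48 readings per basin. Averaging 15 or 16 near-far differences still estimates the same sum when gradient and offset are steady.

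Example: readings of 38.6°C and 37.6°C differ by 1.0°C. A gradient of 1.0°C with no offset fits exactly as well as no gradient with an offset of 1.0°C.

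Now add one reading of both thermometers at a common point, d0 = b_near − b_far. Then (near − far) − d0 = g, and gradient and offset are both estimable. In the example, d0 = 1.0 gives g = 0, and d0 = 0 gives g = 1.0. Keeping both thermometers together throughout would give the offset but never the gradient, so moving them to the two sides afterwards is right.

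The average, (near + far)/2 = μ + (b_near + b_far)/2, still carries any error that the two sensors share. The paired reading does not touch it.

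**2. Possible size**

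Thermometer accuracy is not given, so this part is an assumption: independent errors, each uniform on (−a, a), in a perfectly mixed bath (g = 0). For a threshold t no larger than 2a,

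P(|b_near − b_far| > t) = (1 − t/(2a))²,

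and the probability is 0 when t is 2a or more.

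| Assumed accuracy | Differ by more than 0.5°C | Differ by more than 1.0°C |
|---|---|---|
| ±0.1°C | 0 (largest possible difference 0.2) | 0 |
| ±0.3°C | (1 − 0.5/0.6)² = 0.028 | 0 (largest 0.6) |
| ±0.5°C | (1 − 0.5/1.0)² = 0.250 | 0 (largest 1.0) |
| ±1.0°C | (1 − 0.5/2.0)² = 0.5625 | (1 − 1.0/2.0)² = 0.250 |

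Simulation under the same assumption agrees with the formula.

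**The case against.** Several points on the other side stand.

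- A reader might infer that the study has no data quality control beyond this line. It does: section 18.0 has the local PI review each subject's data, temperature recordings included, and the lead site check completeness; section 24.0 provides one-on-one training in recording. These safeguards are real, but reviewing a complete form does not reveal a constant sensor offset.
- A reader might infer that there is no redundancy at all. That goes too far. Two probes in a circulating bath expose loss or gross failure of one, close agreement is mildly reassuring, and the SVD display partly cross-checks the near thermometer.
- A reader might infer that offset and gradient can never be told apart. A fixed offset stays constant while a heating gradient may change, and the bath starts at room temperature, so early readings could help. The plan does not say that recording starts then or that the readings will be used this way.
- A reader might infer that accuracy is judged against 37-39°C, so that a small offset would turn a fail into a pass. No section says so. That range appears only in section 3.0 as background on standard care; the stated target is 38°C.
- The size rests wholly on assumed accuracy, and with good sensors the problem nearly vanishes. This is a small descriptive study with no planned near-far comparison.
- The data forms and the training email are not in the documents, so an operational check may exist there.

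None of this supplies a step in the documents that separates gradient from offset.

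**Conclusion.** The point holds in limited form. The redundancy claimed in section 17.0 is not delivered by the placement in section 6.0, except against gross failure of one sensor. A steady near-far difference is ambiguous, and the SVD display does not resolve it. The identifiability result assumes constant biases and an SVD that senses its own end of the basin.

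The practical size runs from negligible with accurate thermometers to a difference above 0.5°C in over half of pairs at ±1.0°C. That range reflects the accuracy assumption, not anything known about these thermometers.

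This is an inexpensive improvement to the measurement of a primary outcome, not a flaw that invalidates the study. It is worth making beforehand because the offset cannot reliably be recovered afterwards from the data that the plan collects.

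**What to change.** **Section 6.0.** Add a paired reading: both thermometers at the same point, with both values recorded on the form, before they are attached at the two sides. Do this either in the basin before the SVD is switched on or, before use, in one well-mixed vessel near 38°C. The second option checks the offset close to the temperature of interest and can be done away from the patient.

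**Section 17.0.** Replace the redundancy sentence with this paired check and a stated agreement tolerance beyond which a thermometer is swapped. Choose the tolerance with the instruments' accuracy in view: by the arithmetic above, 0.5°C would reject about 3% of pairs at ±0.3°C but 56% at ±1.0°C.

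**Analysis text, section 17.0.** Report the near-far difference net of the paired offset. State that accuracy against the 38°C target is judged on the thermometers, with the SVD display compared against them.

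**Absolute error.** The paired check removes relative offset only. It cannot show which thermometer is wrong or detect an error common to both. Record the thermometers' stated accuracy, or check one against a reference.

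**Cost.** One extra form row, a brief step per basin (up to four basins, so eight thermometers, for one patient), a spare thermometer, and wording in two sections. The step must not delay rewarming, which favours doing it before use.

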18.0 Provisions to Monitor the Data to Ensure the Safety of Subjects*

- *Describe:*
 - *The plan to periodically evaluate the data collected regarding both harms and benefits to determine whether subjects remain safe. The plan might include establishing a data monitoring committee and a plan for reporting data monitoring committee findings to the IRB and the sponsor.*
 - The data will be reviewed by the local PI each time a subject participates in the study, to confirm standard process and to assess for reported adverse events.
 - As the lead site, we will review all data entered into the database for completeness.
 - *What data are reviewed, including safety data, untoward events, and efficacy data.*
 - Signed informed consent, temperature recordings, water bath treatment time required to achieve rewarming, and adverse events will be reviewed.
 - *How the safety information will be collected (e.g., with case report forms, at study visits, by telephone calls with participants).*
 - Adverse events will be recorded on the data collection form during the treatment of the subject in the emergency department.

PROTOCOL TITLE: Assessment of Sous Vide Water Baths for Acute Rewarming of Frostbitten Extremities.

- Adverse events across all sites will be reviewed at a monthly meeting of collaborating sites.
- *The frequency of data collection, including when safety data collection starts.*
 - Data collection will commence when the subject is treated in the emergency department. Data will be reviewed for safety issues after each subject.
- *Who will review the data.*
 - The PI will review the safety data.
- *The frequency or periodicity of review of cumulative data.*
 - The PI will review cumulative data after each subject.
- *The statistical tests for analyzing the safety data to determine whether harm is occurring.*
 - With an expected subject size of 1-5 study participants in each study location, safety data will be reviewed after each subject participates. There will be no need to make estimations.
- *Any conditions that trigger an immediate suspension of the research.*
 - If 1 or more unanticipated adverse events are considered possibly attributable to the use of the SVD, the study will be put on hold pending review of the incident.
- *Describe the procedures for unblinding study therapy on a subject, including documentation of this in the subject's source document.*
 - Unblinding study therapy will not be necessary, as the study is unblinded to the participant and the clinician treating the subject and the treatment will occur only during the rewarming phase in emergency department visit.

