3.0 Background*

- Frostbite is a clinical entity in which extremities, digits, and appendages undergo freezing damage due to exposure to environmental cold. Once in a safe environment where the potential for re-freezing is minimal, the current standard of care for acute frostbite is the rapid rewarming of the affected body part, using a circulating warm water bath targeted to 37-39°C. There is no current “best” modality to warm and circulate the water. Depending on resources, this may be difficult and time consuming. In the field, water can be heated over a fire and added to a water bath. If heated water is present, hot tap water can be incrementally added to a water bath to achieve and maintain the targeted temperature. In the ED, some have advocated for placing the frostbitten hand or foot in a sink with running hot water and a thermometer in the sink to detect temperature. These methods are difficult at best, and may be dangerous in that they either do not maintain the water at the targeted temperature, or burn the frostbitten and often insensate extremity. An inexpensive, small, and transportable device that could reliably heat and circulate the water would decrease provider effort and optimize the water bath to the targeted temperature range. In remote locations where electricity is present but not reliably hot water, a portable heating device would drastically improve care.
- This modality is novel, and to our knowledge, has only been used clinically by our research group. In early 2020, a study was published investigating the in vitro use of SVDs in creating

PROTOCOL TITLE: Assessment of Sous Vide Water Baths for Acute Rewarming of Frostbitten Extremities.

circulating warm water baths for the rewarming of frozen pigs' feet. In this study, the SVD maintained the water bath at a constant 40°C for 30 minutes and resulted in the rewarming of the pig foot from frozen to pliable. The sous vide modality was compared against and outperformed manual water exchanges. To test this clinically, we completed a pilot study in 2021 and successfully treated acute frostbite in the ED.

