4.0 Study Endpoints*

- The primary study endpoint will be the rewarming of frostbitten extremities for 30 minutes at 38°C.
- The secondary study endpoint will be a survey regarding ease of use of this rewarming modality.
- The primary safety endpoint will be patient pain or discomfort that is determined to be unrelated to the discomfort known to be associated with rewarming frostbitten tissue. Two consecutive temperature measurements above 42°C will prompt the cessation of the SVR.

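### The primary safety endpoint counts only excess pain, and the only study-hold rule covers unanticipated events, so a painless burn from the device is neither counted nor clearly a reason to pause

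*Combined protocol and SAP*

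**What the plan says.** All references are to the combined protocol and SAP.

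- **Safety endpoint (Section 4).** "The primary safety endpoint will be patient pain or discomfort that is determined to be unrelated to the discomfort known" to accompany rewarming. The same bullet adds a 42°C rule that stops the bath. That rule is an instruction for treatment and does not define an outcome.
- **Hold rule (Section 18).** Asked what would suspend the research at once, the plan gives one condition: "If 1 or more unanticipated adverse events are considered possibly attributable to the use of the SVD, the study will be put on hold". The hold lasts until the incident has been reviewed. The plan does not define *unanticipated*.
- **Foreseen hazards (Sections 15 and 20).** Section 15 lists hot water burns and, as unlikely, device failure with electrical injury. Section 20 treats the same injuries as the only foreseeable source of cost to the patient.
- **Sensation and analgesia (Sections 3 and 6).** Section 3 says that manual methods may "burn the frostbitten and often insensate extremity". Section 6 says "Pain increases when water bath temps are above 40°C" and "The provider can provide analgesia as indicated".
- **Examinations and follow-up (Section 6).** "Prior to rewarming, physical examination of the patient, including the frozen extremity, will be completed and documented". The treated limbs are examined again "at 30 minutes to determine warmth and pliability of the tissue, confirming thaw", and completion also depends on the colour of the tissue. At 6 months, "Chart review to assess related complications will also occur at this time".
- **Recording and review (Sections 17 and 18).** Adverse events go on the data form. The PI reviews safety data after each subject, and the sites review adverse events together each month.

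**The concern.** Pain is an incomplete marker for the injury of most interest here. Rewarming hurts in any case, analgesia is allowed, and the protocol describes the limb as often lacking sensation. Section 3 makes that remark about manual methods, but the tissue is the same. A burn under those conditions can occur without the pain that the endpoint requires.

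The hold rule raises a second problem. A safety rule should be clearest for the harm the investigators expect might happen. Here the qualifying word points the other way, because an injury listed in advance is, on an ordinary reading, anticipated.

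At stake is how the safety result is summarised and whether enrolment pauses. Section 3 gives burn as a danger of the manual methods, and Section 15 suggests the device may reduce it. A study that supports that suggestion should count burns directly. Section 6 states that the device is not FDA approved for medical use, and Section 1 anticipates 5-10 further sites. Each local PI would therefore apply an undefined word to the same kind of event.

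**Working it through.** The plan states no figure to reproduce, and no arithmetic applies. The check is to take each foreseeable device injury through the stated rules.

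| Event | Counted in the Section 4 endpoint? | Stops that patient's treatment? | Holds the study under Section 18, read literally? |
|---|---|---|---|
| Burn with pain beyond that of rewarming | Yes | Yes, for excess pain | Arguable: the burn is foreseen, but Section 6 expects no extra discomfort at 38°C |
| Burn without excess pain, two consecutive readings over 42°C | No | Yes, by temperature | No: burns are foreseen in Sections 15 and 20 |
| Burn without excess pain, no such pair of readings | No | Not by the pain or 42°C rule | No, for the same reason |
| Electrical injury | Only through pain | Not by a named rule, unless painful or a medical emergency | Unclear |

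Three points follow.

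1. **Endpoint.** The second and third rows fall outside the endpoint whatever the bath temperature. The 42°C rule changes what happens to the patient and leaves the count unchanged. Such a burn, if noticed, goes on the adverse event form only. Section 17 lists descriptive statistics for the population, time to rewarm and ease of use, with no adverse event summary. The Section 4 endpoint is therefore the only safety outcome the documents define.

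2. **Hold rule.** The other stopping rules (Sections 4, 6, 14 and 15) act on one patient's treatment. Section 18 alone acts on the study. Section 15 supports two readings. It lists burns and electrical injury among potential hazards, which makes them anticipated. It also says any unforeseeable risk would relate to device failure, which would let a PI call a failure-related burn or shock unanticipated. The text does not settle which reading governs.

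3. **Detection.** The 30-minute examination is made against a documented baseline and includes skin colour, so someone looks at the skin. The visible text does not ask that person to record a burn. The data form is not reproduced and may do so.

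**The case against.** The best counter-argument is that the label matters little. The 42°C stop works whether or not the patient feels pain. Two thermometers run continuously, are read every 2 minutes, and are placed partly to find hot spots. The skin is inspected at 30 minutes, adverse events are recorded, and the PI reviews every case. In a study this small, a burn would be discussed individually, and Section 18 says outright that estimates are not needed for safety data. A burn from a bath set at 38°C would usually mean overheating or failure, so a PI might well call it unanticipated and hold the study.

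Most of this stands, and it limits the point. A reader might infer that a device burn would go unseen. The documents do not support that: the safeguards make an unnoticed burn unlikely. A reader might also infer that the hold rule definitely excludes burns and electrical injury. That holds only on the literal reading for burns, and electrical injury is ambiguous.

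What remains is that none of these safeguards puts a painless burn into the safety endpoint or requires a hold. Individual review is the setting in which a clear rule is most useful, because otherwise the decision rests on how each PI reads one word.

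The remedy still relies on the PI's judgement of attribution. That is true, but attribution is a clinical question that the PI can answer from the case. Whether a listed hazard counts as unanticipated is a drafting question that the protocol should answer.

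**Conclusion.** The point holds in a limited form and is worth fixing. Followed as written, the plan would not count a burn without excess pain in its primary safety endpoint, and on a literal reading would not require a hold for it. This rests on two assumptions: that such a burn can occur, which the protocol's own remarks on sensation and analgesia make plausible, and that *unanticipated* is given its ordinary meaning.

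No magnitude should be claimed. A reader might divide one burn by the 5-20 cases expected in Section 2 and quote the result as a hidden injury rate. That would only divide an assumed event by a sample size. The documents give no burn probability, and with a 38°C set point and a 42°C stop it is likely low.

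A reader might also infer from Section 14 that follow-up ends for patients stopped on safety grounds, since withdrawal is said to end data collection. That sentence answers a prompt about subjects who withdraw, and whether it reaches safety stops is unclear. It is an ambiguity to tidy and does not support a finding that follow-up is lost.

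**What to change.** - **Section 4.** Add *thermal or electrical injury possibly related to the SVD* as a safety outcome. Judge it at the existing 30-minute examination against the pre-rewarming examination, and from the adverse event form and the 6-month chart review. Keep excess pain as a separate item.
- **Section 18.** Hold the study for any burn or electrical injury judged possibly attributable to the device, whether or not anticipated, in addition to unanticipated events. Say that blisters on previously frozen skin are recorded and reviewed, but trigger a hold only if the PI judges them a possible burn.
- **Section 14 (optional).** State that safety follow-up continues after a safety stop unless the patient refuses.

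The cost is wording in two sections, or three with the optional change, and at most one item on a data form that may already have it. No new visits or tests are needed. The real downsides are that holds may be slightly more frequent in a small, season-limited study, and that an unblinded PI must tell a burn from frostbite blistering. The documented baseline examination helps with the second.
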